8.3 Correlative Studies

Due to the lack of translational science funding, there are no pre-planned correlative studies. However, study participants will be encouraged to provide biospecimens (i.e. peripheral blood and/or bone marrow specimens) to the Fred Hutch's AML sample repository (FHCRC #1690.00; PI: [name]).

9.0 TOXICITY MONITORING

Both acute and chronic toxicities will be recorded and reported to the PI, and will be reviewed by the independent DMC at scheduled meetings. Monitoring for acute toxicity takes place during and following the administration of the medications. Subjects are observed for the development of an immediate localized allergic reaction or anaphylactic reaction during this time.

Toxicity Criteria

This study will use the CTCAE (NCI Common Terminology Criteria for Adverse Events) Version 5.0 for Toxicity and Adverse Event reporting. A copy of the CTCAE v5.0 can be downloaded from the CTEP home page (<http://ctep.cancer.gov>).

10.0 SUBJECT DISCONTINUATION OF ACTIVE TREATMENT

10.1 Criteria for Removal from Treatment

All reasons for discontinuation of treatment must be documented:

10.1.1 Completion of protocol treatment.

10.1.2 Arrival to the transplant service for planned HCT.

- 10.1.3** Initiation of any leukemia-directed therapy other than protocol therapy
- 10.1.4** Failure to achieve a CR or CRi after 2 courses of therapy with higher-dose G-CLAM or 6 courses of therapy with lower-dose G-CLAM.
- 10.1.5** Persistent aplasia (ANC <500/ μ L or platelets <50,000/ μ L) without evidence of leukemia after Day +49.
- 10.1.6** Relapse after achievement of CR/CRi during treatment.
- 10.1.7** Adverse toxicities that prevent continuation with study treatment.
- 10.1.8** Withdrawal of consent; the patient may withdraw from the study at any time for any reason.

10.2 Duration of Follow-up

Patients will be followed after completion of study treatment to determine event free survival (EFS) and relapse-free survival ([RFS] (for patients achieving CR), as well as overall survival (for all patients) for a maximum of 5 years. Follow-up may include periodic (e.g. every 3 months) review of medical records, and, if absolutely necessary, direct contact of the study participant.

11.0 ADVERSE EVENTS

11.1 Expedited Reporting Requirements

In accordance with Fred Hutch/UW Cancer Consortium IRB policy, all adverse events (AEs; whether occurring on-site or off-site), which in the opinion of the principal investigator (PI) are (1) unexpected, and (2) related or possibly related to the research, and (3) serious or suggests that the research places research participants or others at a greater risk of physical or psychological harm than was previously known or recognized, will be submitted to the IRB within ten (10) calendar days of learning of the problem. Both the “Expedited Reporting Form for Unanticipated Problems or Noncompliance” and the “Adverse Event Reporting Form”, or equivalent forms, will be completed for this reporting.

11.2 Definitions:

- 11.2.1 Adverse Event (AE):** Any harm or untoward medical occurrence in a research participant administered a medical product, medical treatment or procedure even if it does not necessarily have a causal relationship with the product, treatment, or procedure. An adverse event can be any unfavorable and unintended sign (including an abnormal laboratory finding, for example), symptom, or disease temporally associated with the use of a medical product, medical treatment, or procedure whether or not considered to be related. Mechanisms of obtaining information on AE include monthly transcripts, assessment forms obtained after each clinic visit, and hospital progress and discharge notes.

- 11.2.2 Related or Possibly Related AE:** An AE is “related or possibly related to the research procedures” if in the opinion of the principal investigator, it was more likely than not caused by the research procedures. AEs that are solely caused by

an underlying disease, disorder or condition of the subject or by other circumstances unrelated to either the research or any underlying disease, disorder or condition of the subject are not “related or possibly related”. If there is any question whether or not an AE is related or possibly related, the AE should be reported.

11.2.3 Serious AE (SAE): An adverse event that results in any of the following outcomes:

- Death
- Life-threatening adverse event (real risk of dying)
- Prolongation of hospitalization*
- Persistent or significant disability/incapacity/or change in psychosocial status
- Congenital anomaly
- Requirement of intervention to prevent permanent impairment of damage

*Hospitalization itself will not be considered a serious adverse event if required for complications of AML or comorbid conditions. Hospitalization will be considered a SAE if it fulfills the criteria for a serious and unexpected adverse event as otherwise described.

11.2.4 Unexpected AE: An unexpected adverse event is defined as an event that has a nature or severity, or frequency that is not consistent with the applicable investigator brochure, or the prior medical condition of the subject or other treatment given to the subject. “Unexpected,” as used in this definition, refers to an adverse drug experience that has not been previously observed and reported in preclinical or clinical studies rather than an experience that has not been anticipated based on the pharmacological properties of the study drug.

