8.2.3 Assessment of cost

The costs associated with inpatient and outpatient management will be calculated using electronic billing information from the UWMC and SCCA. Costs will be converted from charges using departmental cost-to-charge ratios. We anticipate reporting descriptive information identifying major cost drivers and total/subset costs per phase of treatment (i.e. induction, outpatient management, and readmission), similar to our approach used previously.^{21,22}

8.2.4 Examination of patient and physician attitudes towards medical decision-making and treatment allocation

8.2.4.1 We will explore patient-reported factors influencing medical decision-making through a Patient Preference Survey (APPENDIX D) distributed on study enrollment. This survey will include a question on whether they agree to be randomized or prefer to choose their treatment arm, and explores the reasons underlying this decision. As above, given that patients do not always fill out questionnaires, we will measure percentage of returned responses regarding reasons for treatment decision-making as one of our feasibility outcomes. Surveys not returned will not be considered a protocol deviation.

8.2.4.1 We will also explore physician preferences towards treatment-intensity randomization through a Physician Preference Survey (APPENDIX E) also distributed on study enrollment. This survey includes questions about whether the physician was agreeable to randomization (even if the patient was not) and explores reasons the physician might have not wanted to randomize the patient. As physicians are extremely busy, we will measure percentage of returned responses regarding reasons for treatment decision-making as one of our feasibility outcomes. Surveys not returned will not be considered a protocol deviation.

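### New hospitalization is missing from the SAE outcomes in 11.2.3, and the circular footnote adds unexpectedness, so a toxicity admission is not an SAE on the ground of hospitalization alone

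*Combined protocol and SAP*

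**What the plan says.** Section 11.2.3 of the protocol defines an SAE as "An adverse event that results in any of the following outcomes". Six outcomes follow: death, a life-threatening event, prolonged hospitalization, persistent disability (or a change in psychosocial status), congenital anomaly, and "Requirement of intervention to prevent permanent impairment of damage". The hospital item reads "Prolongation of hospitalization" and carries an asterisk.

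The footnote has two sentences. The first is an exclusion: "Hospitalization itself will not be considered a serious adverse event if required for complications of AML or comorbid conditions". The second is an inclusion: "Hospitalization will be considered a SAE if it fulfills the criteria for a serious and unexpected adverse event as otherwise described".

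Four other places bear on this:

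- Section 11.1 requires expedited reporting to the IRB when the principal investigator considers an event unexpected, and related or possibly related, and either serious or suggestive of greater risk than was known.
- Section 11.2.4 says that unexpected "refers to an adverse drug experience that has not been previously observed and reported in preclinical or clinical studies".
- Section 11.4 records grade ≥3 non-hematologic events. It reports myelosuppression and its complications, including the resulting admissions, only as an annual summary.
- Section 8.2.3 names "induction, outpatient management, and readmission" as phases of treatment for costing.

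**The concern.** The list and its footnote do not fit together. The first footnote sentence exempts certain admissions, which is needed only if admission normally counts, yet no listed item makes it count. The second sentence appears to supply the missing rule but sends the reader back to criteria that do not include admission. It also makes unexpectedness part of the test, while 11.1 treats unexpected, related and serious as separate conditions.

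At stake is whether an event's classification depends on where the patient was when it occurred. A drug toxicity that lengthens an inpatient stay matches a listed outcome. The same toxicity that brings an outpatient into hospital does not. Because seriousness is one limb of 11.1, the gap can also reach expedited reporting. The case is realistic, since 8.2.3 foresees both outpatient care and readmission.

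**Working it through.** No arithmetic applies; the check is to run cases through the text. Take an outpatient between cycles with a grade 3 non-hematologic drug toxicity who is admitted, treated and discharged without lasting harm.

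1. **The list in 11.2.3.** The event is not fatal, life-threatening or disabling, involves no congenital anomaly, and needs no intervention to prevent permanent impairment. There was no existing stay to prolong. None of the six outcomes is met.
2. **Footnote, first sentence.** The admission is due to drug toxicity, not to complications of AML or a comorbid condition. It is not excluded.
3. **Footnote, second sentence.** The admission counts if the event is serious and unexpected as described elsewhere. The only seriousness criteria described are the six in step 1, and none is met. It is not included.

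The admission is therefore neither excluded nor included, and hospitalization by itself gives no ground for calling the event an SAE.

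Now vary the case:

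- **The event also meets another listed outcome.** It is an SAE through that item, because any one outcome suffices.
- **The toxicity lengthens the stay once the patient is in hospital.** The prolongation item can then apply.
- **The toxicity is already known.** All four drugs are commercial (7.0), and 7.1 to 7.4 list their known adverse effects. Under 11.2.4 such an event would normally not be unexpected, so the footnote's second sentence would not admit it even if hospitalization were added to the list. The missing item and the added expectedness are thus two separate defects, and both need correction.

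For expedited reporting, the condition in 11.1 is: unexpected AND (related or possibly related) AND (serious OR suggests greater risk).

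- **Known toxicity:** fails the first condition however seriousness is defined. The gap changes nothing here.
- **Unexpected, related admission that meets another listed outcome:** serious, hence expedited. The gap changes nothing here either.
- **Unexpected, related admission that meets no other listed outcome:** not serious as written. It is expedited only if the principal investigator judges that it suggests greater risk than was known.

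The third case is the whole effect on expedited reporting. For SAE classification the effect is wider and includes admissions for known toxicities.

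Other capture in the protocol: 11.4 records and grades non-hematologic events of grade ≥3 whether or not they are SAEs, and sends those not expedited to the IRB at annual renewal. Section 8.2.2 collects reasons for hospitalization, ICU need and length of stay. The primary endpoint (14.3.1) is willingness to be randomized. The monitoring rules (14.4) use death by day 28 and MRD-negative CR. None of these uses an SAE count.

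**The case against.** The strongest reply is that this is a wording gap with little consequence. Any one outcome suffices, so the more dangerous toxicity admissions are SAEs already. The second footnote sentence says that a qualifying hospitalization counts; it does not say that only such a hospitalization counts. Since the first sentence excludes only two kinds of admission, the rest can be read as meant to count. Events of grade ≥3 and reasons for hospitalization are recorded in any case, and every condition in 11.1 rests on the principal investigator's opinion, so relying on the greater-risk clause is nothing unusual.

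Much of this stands. A reader might infer that an outpatient's toxicity admission has no route to being an SAE; the documents do not support that, for the reasons just given. A reader might also infer that the arms would be affected differently, because consolidation can run to 12 cycles on the lower-dose arm against 4 on the higher-dose arm (6.6). The protocol does not say where either arm's cycles are given or how outpatient time compares, so this is conjecture. Nor can one say that toxicity in general would be under-represented: what is at risk is the SAE label and one limb of expedited reporting.

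The asterisk also sits on the prolongation bullet, so the footnote might qualify prolonged stays too. That would make the contrast between inpatients and outpatients less certain, but it would leave new admissions where they are and extend the expectedness problem to prolonged stays.

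What does not stand is the suggestion that the text needs no repair. An ambiguous definition of seriousness leaves staff to decide case by case, and no other section resolves it.

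**Conclusion.** The point holds as a defect in a safety definition. As written, a toxicity admission of an outpatient is not an SAE on the ground of hospitalization alone, and the footnote improperly mixes unexpectedness into seriousness. Two things follow: SAE classification of such admissions is incomplete or uncertain, and an unexpected, related admission meeting no other criterion falls outside the serious limb of 11.1.

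The number of affected events cannot be derived from the documents. They are admissions for drug toxicity that meet no other listed outcome, among at most 50 patients, each of whom may have several cycles. No sample size, power figure, endpoint or stopping rule changes.

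The conclusion rests on two assumptions: that the footnote's reference to criteria described elsewhere means the six outcomes in 11.2.3, the only seriousness criteria given; and that some patients are admitted from outpatient care, which 8.2.3 foresees. The change should be made, since it is simple and the definition governs safety reporting.

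**What to change.** In 11.2.3:

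- Change the bullet to *Hospitalization or prolongation of hospitalization*, with its asterisk kept.
- Keep the footnote's first sentence, which exempts admissions for complications of AML or comorbid conditions.
- Replace the second sentence with: *Any other hospitalization due to an adverse event is an SAE, subject to 11.4.* The reference to 11.4 preserves its handling of myelosuppression-related admissions.
- Leave expectedness to 11.1 and 11.2.4.

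The cost is two wording changes and a small number of additional SAE records. Little new data collection is needed, because reasons for hospitalization are already gathered under 8.2.2.

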11.3 Grading Adverse Event Severity

All AEs will be graded in severity according to the NCI Common Terminology Criteria for Adverse Events (CTCAE) Version 5.0 (<http://ctep.cancer.gov>). If a CTCAE criterion does not exist, the investigator should use the grade or adjectives: Grade 1 (mild), Grade 2 (moderate), Grade 3 (severe), Grade 4 (life-threatening), or Grade 5 (fatal) to describe the maximum intensity of the adverse event.

11.4 Monitoring, Recordings, and Standard Reporting of Adverse Events

Only grade ≥ 3 adverse events other than hematologic toxicities will be recorded, graded, and reported as appropriate per 11.1. AEs will be collected for the duration that the patient remains on protocol. If a subject decides to terminate the study early their medical record will continue to be followed for AEs for up to 4 weeks after the treatment was given or they start a new anti-leukemia therapy, whichever occurs first. AEs that do not meet the requirement for expedited reporting will be reported to the IRB as part of the annual renewal of the protocol. Myelosuppression and associated complications are expected events during leukemia therapy; therefore, myelosuppression and associated complications such as fever, infections, bleeding, and related hospitalizations will not be reported as individual AE but will be summarized in the annual report to the IRB.

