14.4 Monitoring for efficacy and early mortality

This study will evaluate each regimen separately, and also compare regimens among patients who are randomized. Details for both sets of analyses are provided below.

Within-arm monitoring for efficacy and early mortality

We will enroll patients in 2 stages in order to allow for early stopping for unacceptable differences in early mortality or inefficacy. Early mortality will be defined as death for any reason on or before day 28 after starting therapy. Inefficacy will be evaluated using MRD^{neg} CR.

We will use our ongoing clinical trial using a CPX-351 in medically less fit adults with AML or high-grade MDS will provide “historical” control data for both inefficacy and early mortality. In this trial (FHCRC #2642.00), which used essentially identically inclusion/exclusion criteria, we have so far treated 37 subjects at a CPX-351 dose of 32 units/m². Among these, 8 patients achieved an MRD^{neg} CR (22%). Ten patients (27%) died within 28 days of treatment initiation; at least 4 of these subjects experienced early disease progression as main cause of death, highlighting the balance between treatment efficacy and potential toxicity.

In the first stage, 10 patients will be accrued to each arm, either in a randomized or non-randomized fashion. Each arm will be evaluated separately for early death and inefficacy stopping rules. Accrual may temporarily be held while outcome data on these patients matures.. As some patients may choose to not be randomized, the 2 treatment arms may be evaluated at a different time point for early stopping.

1) Lower-dose Arm: After 10 patients have been accrued to the lower-dose arm, we will evaluate for early death and inefficacy.

Early death: If the number of early deaths is 5 or higher, accrual will stop with the conclusion that the arm is too toxic for further randomization. If the true early mortality rate is 30% or less, the probability of observing 5 or more early mortality events is 15%.

Inefficacy: If there are 0 patients with MRD^{neg} CR, accrual will stop with the conclusion that the arm is not efficacious enough for further randomization. If the true MRD^{neg} CR rate is 22%, the probability of observing 0 MRD^{neg} CRs in 10 patients is 8%.

2) Higher-dose Arm: After 10 patients have been accrued to the higher dose arm, we will evaluate for early death and inefficacy.

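### Section 11.4 makes no exception for fatal infection or bleeding linked to myelosuppression, and no pre-specified mortality rule covers deaths after day 28

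*Combined protocol and SAP*

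**What the plan says.** **Reporting.** Section 11.4 opens with a general rule: "Only grade ≥ 3 adverse events other than hematologic toxicities will be recorded, graded, and reported as appropriate per 11.1". It ends with an exemption. The reason given is that "Myelosuppression and associated complications are expected events during leukemia therapy", and the consequence is that "associated complications such as fever, infections, bleeding, and related hospitalizations will not be reported as individual AE"; a summary in the yearly IRB report takes their place. The exemption names no grade. Section 11.2.3 puts death among the outcomes that make an event serious, and 11.3 defines Grade 5 as fatal, but the exemption refers to neither.

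Expedited reporting to the IRB within ten calendar days (11.1) needs three conditions together. The event must be "1) unexpected, and (2) related or possibly related to the research, and (3) serious or suggests that the research places research participants or others" in more danger than was known. Section 11.2.4 defines the first condition: "An unexpected adverse event is defined as an event that has a nature or severity, or frequency that is not consistent", judged against the available product information, the patient's prior condition or other treatment. Its second sentence then narrows the term to experiences not already seen and reported in earlier studies.

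**Committee review.** Section 9.0 says: "Both acute and chronic toxicities will be recorded and reported to the PI, and will be reviewed by the independent DMC at scheduled meetings". Section 12.0 has the Consortium DSMC, the scientific review committee and the IRB look at the protocol every year at minimum and otherwise when needed, with adverse events and stopping rules in scope. Section 12.0 does not mention the DMC of 9.0. Neither section gives that DMC's meeting interval or says what data it receives.

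**Mortality rules.** Section 14.4 says: "Early mortality will be defined as death for any reason on or before day 28 after starting therapy". That endpoint feeds a within-arm rule (accrual stops at 5 or more early deaths among the first 10 patients) and a between-arm Fisher's exact test at the 10% level once each arm has at least 10 patients.

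**The concern.** The trial compares two chemotherapy intensities in patients admitted because their TRM score is 13.1 or higher, that is, because their predicted risk of early death is high. Infection and bleeding during myelosuppression are among the likeliest ways for the arms to differ in harm. Treatment also runs well past the first course: re-induction is allowed, followed by up to 4 consolidation courses on the higher-dose arm or 12 on the lower-dose arm (6.6).

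Read together, 11.4 and 14.4 allow a death from sepsis or hemorrhage in a later course to trigger no stopping rule and to generate no individual report to the IRB. At stake is whether an imbalance in such deaths between arms would be noticed promptly and in a form that shows arm, course and cause.

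**Working it through.** **1. The plan's own figure.** Section 14.4 gives 15% as the chance of 5 or more early deaths in 10 patients at a true rate of 30%. With X ~ Binomial(10, 0.30), P(X ≥ 5) = 0.1503. The figure reproduces, and the arithmetic of the rule is not in question.

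**2. What the 28-day window covers.** The response marrow is taken at count recovery or between Days +28 and +35, whichever comes first (6.5). Re-induction and consolidation follow that marrow. A re-induction begun after recovery before day 28 would fall partly inside the window; otherwise later courses lie outside it. Section 14.4 describes no mortality look after the first-stage looks, although accrual may go on to 50. Section 17.0 refers to section 10.0, which lists reasons for taking an individual patient off treatment and contains no study-level mortality rule.

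**3. Tracing one event.** Take a fatal neutropenic sepsis in a consolidation course.

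- First sentence of 11.4: it is non-hematologic and of grade 3 or more, so it is recorded, graded and reported as 11.1 requires.
- Last sentence of 11.4: it is a complication of myelosuppression, so it is not reported individually and goes into the annual summary.
- 11.1: it must be unexpected, and 11.4 has declared the class expected. The severity and frequency wording of 11.2.4 could bring it back in, but the next sentence of 11.2.4 works against that. Section 1.0 already reports a septic-shock death on G-CLAM, and 7.3.3 lists sepsis and death for cytarabine. Expedited reporting is therefore uncertain.
- 14.4: it occurs after day 28, so it is not counted.
- 9.0: the DMC should see it, at an unstated time and in an unstated form.
- 10.2: the death is captured for overall survival, as an outcome.

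**4. Illustration of what the 28-day rule cannot see.** Inputs: 28-day mortality e, set at the historical 10/37 = 27% (14.4) and at lower assumed values; and q, the share of day-28 survivors who later die of treatment toxicity. The documents give no value for q, so 10%, 20% and 30% are assumptions. The total counted is t = e + (1 − e)q; for example 0.27 + 0.73 × 0.20 = 0.416. The table compares P(X ≥ 5) for Binomial(10, e), which is the present rule, with Binomial(10, t), which is the same count if later toxic deaths were included and all ten patients had been followed through later treatment.

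| e | Present rule | q = 10% | q = 20% | q = 30% |
|---|---|---|---|---|
| 10% | 0.2% | t = 19%: 2.7% | t = 28%: 11.8% | t = 37%: 29.4% |
| 20% | 3.3% | t = 28%: 11.8% | t = 36%: 27.1% | t = 44%: 47.0% |
| 27% | 10.4% | t = 34.3%: 23.3% | t = 41.6%: 40.8% | t = 48.9%: 59.6% |

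The present rule's probability is the same for every q. The table shows that insensitivity. It does not propose a new boundary, and t mixes deaths of any cause to day 28 with later toxic deaths (at least 4 of the 10 historical early deaths were mainly due to disease progression).

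**The case against.** The case on the other side has real substance.

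- **The 28-day window is reasoned.** Section 1.0 reports, from 3,365 patients, that the weekly risk of death drops steeply after 4 weeks from the start of intensive induction, and the historical control is a 28-day rate. This justifies the window for an induction stopping rule, and that stands. It does not address how deaths in later courses are listed and reviewed.
- **Exempt from individual reporting does not mean unrecorded.** Section 11.4 collects adverse events while the patient is on protocol, and its first sentence has grade 3 and higher non-hematologic events recorded. The exemption speaks of the IRB report and does not say what the DMC receives. This stands, but the two ends of 11.4 still need reconciling.
- **Silence on Grade 5 is not an explicit inclusion of fatal events.** True, but the exemption is worded without limit, and a site applying it literally would include them.
- **The scope is narrow.** Cardiac, hepatic, neurologic and other toxic deaths unrelated to myelosuppression are not exempt. The primary endpoint, willingness to be randomized, does not depend on late deaths. Both stand.

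Three stronger readings are tempting, and the documents do not support them. A reader might infer that late toxic deaths reach reviewers only in the annual summary; 9.0, 12.0 and the survival follow-up in 10.2 contradict that. A reader might infer that each arm's toxicity conclusion rests on course 1 alone; adverse events are collected throughout protocol treatment, and 8.2.2 collects infections, bleeding and ICU care. A reader might compound an assumed fatal risk per course over the maximum number of courses. No per-course risk is given, treatment ends early for relapse, transplant or toxicity (10.1), and the maximum itself is inconsistent: 6 + 12 = 18 lower-dose courses under 6.0 and 10.1.4, but 2 + 12 = 14 under 6.5.3 and 6.6. Those sections must be reconciled as a separate matter.

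**Conclusion.** The point holds in limited form. Section 11.4 exempts infections and bleeding associated with myelosuppression from individual reporting without excepting fatal ones, and this pulls against its own first sentence, 11.2.3 and 9.0. Such a death may also miss the expedited route. No pre-specified mortality rule covers most deaths in re-induction or consolidation. Their review depends on DMC meetings of unstated interval and content, on as-needed review, and on the annual summary.

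The gap is in how clearly and how quickly such deaths are brought to review; monitoring is not absent. Its size cannot be estimated from the documents, since they give no late toxic death rate, and the table above is conditional on assumed values. The change is worth making because it is cheap and concerns a central safety contrast in a high-risk population.

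**What to change.** Add to 11.4 that the exemption does not apply to Grade 5 events, and that every death on protocol, or within 28 days after the last dose of any course, is recorded individually with arm, course number and cause. List these deaths by arm and course at each DMC or DSMC review, and place the same list beside the day-28 deaths at the 14.4 looks. The committee listing will carry most of the weight, because 14.4 describes no look after the first-stage ones. It would also help to state in 9.0 or 12.0 how often the DMC meets and that it receives this listing.

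No stopping boundary, dose or treatment rule changes. The cost is a few extra individual reports and one listing. Deaths are already followed for overall survival under 10.2, so the added work is extracting cause and course number from the source documents into the study database.
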